#### 4.1.4.3 Temporary treatment interruption and dose reduction

DLTs or those AEs requiring dose adjustment as indicated within the prescribing information, should be managed by treatment interruptions and subsequent dose reductions of the presumed causal study drug(s) according to the schedule described in [Table 4.1.4.3: 1](#). Please also refer to Section 4.2.3 for additional recommendations. In Part A, both Xentuzumab (BI 836845) and afatinib must be paused when a DLT occurs during the first treatment course. Dose reductions will apply to individual patients only and dose of Xentuzumab (BI 836845) and/or afatinib may be reduced independent of one another. Once the dose has been reduced, it cannot be increased later.

To prevent the development of more severe adverse events, treatment related AEs should be closely monitored and managed early and proactively as described in [Section 4.2.3](#).

Treatment should be paused until a patient has recovered from a drug-related AE to grade  $\leq 1$  or baseline. Baseline is defined as the CTCAE grade at the start of treatment. For patients who develop a DLT, treatment may be resumed at reduced dose according to the dose reduction scheme of the patient's starting dosage (Table 4.1.4.3: 1). If a patient has not recovered to Grade  $\leq 1$  or baseline within 14 days, study treatment must be permanently discontinued. In the event that the patient is deriving obvious clinical benefit according to the investigator's judgment, further treatment with study drug(s) will be decided in agreement between the sponsor and the investigator.

Diarrhoea and skin-related AEs are common side-effects of afatinib listed within the prescribing information. Please refer to the current afatinib prescribing information/SmPC for dose adjustment recommendations (except for the Course 1 of Part A if a DLT occurs, in which case both drugs need to be interrupted until AE recovery, refer to [Section 5.2.6](#)). When these AEs occur and are considered related to study treatment, the first dose modification is recommended to be made preferentially for afatinib.

In the event of any unrelated AEs or related non-DLT AEs, the investigator may choose to interrupt the medication (Xentuzumab (BI 836845) and/or afatinib) for up to 14 days, but no dose reduction should occur unless indicated in the current drug label/SmPC of afatinib. If the medication is interrupted for more than 14 days, the decision to continue with

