Proprietary confidential information.

© 2016 Boehringer Ingelheim International GmbH or one or more of its affiliated companies. All rights reserved.  
This document may not - in full or in part - be passed on, reproduced, published or otherwise used without prior written permission.

Xentuzumab (BI 836845) and/or afatinib will be made by the BI clinical monitor in agreement with the investigator.

Applicable dose levels for weekly Xentuzumab (BI 836845) are 1000 mg and 750 mg. For afatinib, the applicable dose levels are 40 mg, 30 mg, and 20 mg. No dose reduction is allowed below 750 mg for Xentuzumab (BI 836845) or below 20 mg for afatinib. Patients who need further dose reduction which is not allowed according to protocol should be discontinued from that drug treatment. An exception to this rule can be considered upon discussion with BI's Clinical Monitor in patients who derive obvious clinical benefit according to the investigator's judgement. Alternative dose modification scheme can only be considered after discussion and agreement between the investigator and the BI clinical monitor.

Management of afatinib related adverse reaction and dose adjustment should be based on the European SPC or current prescribing information for afatinib of the respective country or institutional standard if not specified by protocol.

During temporary treatment interruption of Xentuzumab (BI 836845), the scheduled drug infusion will be skipped and will not be retrospectively administered.

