### **4.3 TREATMENT COMPLIANCE**

Xentuzumab (BI 836845) will only be administered by trained staff in participating sites. Date and time of start and end of infusion, the exact amount of drug administered at each infusion will be documented in the eCRF/ study medication form.

Afatinib will be given in accordance with the protocol and the instructions of a site investigator.

The appropriate number of afatinib tablets for 4-week treatment course will be provided to patients to be self-administered at home. Patients will be asked to bring the remaining trial medication at the end of each 4-week course to the investigator site for a compliance check. The remaining film-coated tablets will be counted by the investigator/site staff and recorded at the investigator site. Discrepancies between the number of tablets remaining and the calculated number of tablets the patients should have taken must be documented and explained. At the end of each 4-week course, any remaining medication will be collected. If the patient is eligible for further treatment, a new bottle of study medication must be dispensed.

The investigator and/or the sponsor can withdraw a patient from the study in the event of serious and persistent non-compliance which jeopardizes the patient's safety or render study results for this patient unacceptable. For afatinib, a maximum of 6 consecutive doses or 7 non-consecutive doses may be missed for other reasons than drug-related AEs. Patients who miss afatinib treatment more frequently are considered non-compliant.

Afatinib should not be taken more than once a day. Patient experiencing emesis should not take a replacement dose.

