## 6.2.2 Treatment period

Every treatment course is 28 days. In case a patient misses the scheduled study visit but reports to the investigative site before the next scheduled study visit, the missed visit will be performed. The current date and reason for the delayed visit will be noted in the source documentation. All subsequent study visits should take place at the next scheduled visit the [Flow Chart](#). In the event of any study drug interruption or delay of treatment, the tumour assessment scheduled will not be changed. The missed scheduled Xentuzumab (BI 836845) administration will be skipped if the patient reports to the investigator outside the time window specified in Flow Chart.

In this trial, patients may be hospitalized for the day of treatment and PK sampling at the discretion of the investigator; patients may be discharged if tolerated the treatment well and no safety concerns are present as judged by the investigator.

Refer to the Flow Chart for procedure details.

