For afatinib, this is calculated as the total duration of treatment with this medication in days multiplied by the actual dose taken (using the actual dose recorded on the Case Report Form (CRF)) for the days the medication was taken. This takes into account the dose reductions of afatinib. This calculation is only an approximation of the total dose taken, since the way the data are collected do not allow a more precise calculation.

Dose intensity of specific trial medication during all treatment duration (%):

Dose intensity of trial medication will be calculated separately for xentuzumab and afatinib.

$100 * (\text{Total dose of specific trial medication actually received by a patient} / \text{Planned total dose of specific trial medication during the entire duration of treatment})$.

The planned total dose is calculated as the total dose of the medication a patient should have received from the date of first administration of the medication to the date of last administration.

The planned total dose of xentuzumab for each patient is calculated using the following formula: planned dose per infusion (e.g. 1000 mg) multiplied by number of visits with administration of xentuzumab.

For afatinib, the planned total dose for each patient is calculated using the following formula: total duration of treatment with this medication in days multiplied by the planned daily dose (e.g. 40 mg, using the dose the patient was initially assigned to).

This is done assuming that the initial dose was taken throughout, and dose reduction as specified in the protocol will not be considered in the calculation. This means that if a patient had protocol-defined dose reduction due to an Adverse Event (AE), the reduced dose will not be used in the calculation of the denominator.

For afatinib, this calculation is only an approximation of the dose intensity, since the way the data are collected does not allow a more precise calculation.

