7.3 TREATMENT COMPLIANCE

Compliance was not analysed separately, but assessed in terms of exposure (including dose intensity). Refer to [Section 7.7](#) for further details on exposure analysis.

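### The xentuzumab dose-intensity denominator in SAP 5.4.2 counts only infusions that were given, so skipped infusions cannot lower the percentage

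*SAP*

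**What the plan says.** SAP 5.4.2 (Treatment exposure) defines dose intensity, separately for each drug, as 100 times the total dose received divided by the planned total dose. The denominator is first defined in general terms: "The planned total dose is calculated as the total dose of the medication a patient should have received from the date of first administration" through to the date of the last one. The xentuzumab rule that follows is "planned dose per infusion (e.g. 1000 mg) multiplied by number of visits with administration of xentuzumab". The afatinib rule is "total duration of treatment with this medication in days multiplied by the planned daily dose". The xentuzumab numerator is the sum of the doses administered over all courses.

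The protocol fixes weekly infusions on days 1, 8, 15 and 22 of each 28-day course (4.1.1.1). For events that are unrelated, or related but not DLTs, the investigator may interrupt either or both drugs "for up to 14 days, but no dose reduction should occur unless indicated in the current drug label/SmPC of afatinib" (4.1.4.3). During a xentuzumab interruption, "the scheduled drug infusion will be skipped and will not be retrospectively administered" (same section). Protocol 6.2.2 adds that a missed xentuzumab "administration will be skipped if the patient reports to the investigator outside the time window specified in Flow Chart".

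SAP 7.3 plans no separate compliance analysis and refers instead to exposure, dose intensity included. SAP 7.7 summarises the exposure variables by dose cohort.

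**The concern.** The general definition and the xentuzumab formula agree only when no infusion is omitted between the first and the last. The protocol expects omissions and says they are not made up. Each one leaves the numerator and the denominator together, so the percentage cannot fall because of it.

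A patient whose xentuzumab was withheld for two weeks and then resumed at full dose would be reported at 100%. The calendar-based afatinib denominator keeps paused days, so the same pause would lower afatinib dose intensity and leave xentuzumab's unchanged. The two percentages would then be reported on different bases.

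What is at stake is the reported delivery of the investigational antibody, in a trial that asks whether the combination can be tolerated. The figure would look more favourable than the SAP's own definition allows.

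**Working it through.** The documents state no dose-intensity figure, so there is none to reproduce. The check applies both denominators to assumed infusion patterns.

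**Inputs**
- Assigned dose 1000 mg per infusion and a reduced level of 750 mg (Protocol 4.1.1.1 and 4.1.4.3).
- Four scheduled infusions per 28-day course (Protocol 4.1.1.1).
- A 14-day interruption, equal to two weekly infusions (Protocol 4.1.4.3).
- The number and placing of skips are assumptions. All skips lie between the first and last administration.

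**Formulas**
- SAP formula: 100 × dose given / (1000 × infusions given).
- SAP definition: 100 × dose given / (1000 × infusions scheduled from first to last).

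If *s* of *n* scheduled infusions are skipped and the rest are given in full, the first is always 100% and the second is 100 × (*n* − *s*)/*n*.

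| Pattern | Dose given (mg) | SAP formula | SAP definition |
|---|---|---|---|
| 8 scheduled, none skipped | 8000 | 8000/8000 = 100% | 8000/8000 = 100% |
| 8 scheduled, 1 skipped | 7000 | 7000/7000 = 100% | 7000/8000 = 87.5% |
| 8 scheduled, 2 skipped | 6000 | 6000/6000 = 100% | 6000/8000 = 75.0% |
| 8 scheduled, 4 skipped | 4000 | 4000/4000 = 100% | 4000/8000 = 50.0% |
| 12 scheduled, 2 skipped | 10000 | 10000/10000 = 100% | 10000/12000 = 83.3% |
| 16 scheduled, 2 skipped | 14000 | 14000/14000 = 100% | 14000/16000 = 87.5% |
| 24 scheduled, 2 skipped | 22000 | 22000/22000 = 100% | 22000/24000 = 91.7% |
| 8 scheduled, none skipped, 4 at 1000 and 4 at 750 | 7000 | 7000/8000 = 87.5% | 7000/8000 = 87.5% |
| 12 scheduled, 4 at 1000, 2 skipped, 6 at 750 | 8500 | 8500/10000 = 85.0% | 8500/12000 = 70.8% |

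The last two rows show that the formula does register dose reductions, but misses skips even when reductions are also present.

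**Comparison with afatinib.** Suppose both drugs are paused for 14 days within three courses (84 days, 12 scheduled infusions). Afatinib at 40 mg gives (70 × 40)/(84 × 40) = 2800/3360 = 83.3%, counting in the numerator only the days on which it was taken. Xentuzumab gives 100% by the SAP formula and 10/12 = 83.3% by the SAP definition.

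**Limit of the effect.** Infusions omitted after the last administration create no discrepancy, because the definition itself stops at the last administration.

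**The case against.** The strongest reply is that the phrase could mean visits at which the Flow Chart schedules xentuzumab, given that it directly follows a definition based on what should have been received. On that reading nothing is inconsistent. The words do not say this, however, and a programmer following them would count infusions given. If scheduled visits were meant, the sentence still needs rewording.

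A second reply is that skips can be seen elsewhere. SAP 5.4.2 also reports the number of infusions, the duration of xentuzumab exposure and the number of courses started, and violation code C2 in SAP Table 6.2:1 covers medication not given per protocol. It is true that the information is not lost. But cohort-level summaries of counts and durations do not correct the percentage, and a skip that the protocol permits need not be flagged under C2.

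Third, the afatinib contrast is less firm than its arithmetic suggests. The SAP describes the afatinib numerator by treatment duration as well as by days taken, and calls that calculation approximate. This qualification stands, and the contrast is only supporting evidence. The SAP attaches no such caveat to xentuzumab.

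Finally, no decision depends on the figure. The RP2D safety analysis in SAP 9.1 draws on treatment duration and on patients with dose reductions, not on dose intensity. That stands, and it limits the severity.

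**Conclusion.** The concern holds. Taken at its wording, the xentuzumab formula departs from the SAP's own definition whenever an infusion is skipped between first and last dose, and the error is always upward. For a single 14-day pause without reduction, the overstatement is 25.0 percentage points over 8 scheduled infusions (100 − 75.0), 16.7 over 12 (100 − 83.3) and 8.3 over 24 (100 − 91.7). These are illustrations on assumed patterns. Without a skip rate in the documents, the trial-level distortion cannot be estimated.

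The effect is confined to descriptive exposure reporting and to the compliance assessment that rests on it. MTD, RP2D selection, objective response and sample size are untouched. It should be corrected, but it does not threaten the trial's main conclusions.

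**What to change.** Redefine the xentuzumab planned total dose in SAP 5.4.2 as the initially assigned dose per infusion times the number of weekly infusions scheduled from first to last xentuzumab administration. That number can be computed as round((last infusion date − first infusion date)/7) + 1. With the first infusion as anchor, the Flow Chart window of ±2 days moves the quotient by at most 2/7 = 0.29, so rounding recovers the scheduled count. A check over 1 to 105 scheduled infusions, with the last visit shifted by −2 to +2 days, found no miscounts. This applies the definition already in the SAP and puts xentuzumab on the same calendar basis as afatinib. A tabulation of skipped infusions per patient would be a useful optional addition.

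The cost is one sentence in the SAP and one line of programming. No new data are needed, since Protocol 4.3 already provides that "Date and time of start and end of infusion, the exact amount of drug administered at each infusion will be documented". The only drawback is that reported dose intensity will be less favourable wherever infusions were skipped. No dose or clinical rule changes.

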6 GENERAL ANALYSIS DEFINITIONS

6.1 TREATMENTS

Part A and part B: Patients will be analysed according to the cohort initially assigned. All planned analysis will be presented by this cohort, unless specified otherwise. Handling of patients where cohort assignment has not been followed will be handled on a case-by-case basis, to be agreed at report planning meetings or DBL meeting (but prior to database lock).

For safety summaries data recorded during the Residual Effect Period (REP) will be considered as on-treatment. For this trial, the length of the REP is 42 days.

The actual study periods and treatment codes are defined in a document entitled “8-07-other-sdtm-trial-arms-trial-elements”, which can be found in Data Management and Statistics (DMS) folder, Section 8, within BIRDS.

6.2 IMPORTANT PROTOCOL VIOLATIONS

No per protocol set (PPS) analysis will be performed for this study, hence, no patient will be excluded from the analyses (except those with missing informed consent or not adhering to age limit). However patients with potentially important protocol violations (IPVs) will be documented. The following list of potentially IPVs in Table 6.2: 1 will be used; note that this is a working list and may not be finalised until the final Blinded Report Planning Meeting (BRPM) or DBL meeting (but prior to database lock for the primary analysis). Potentially important protocol violations will be handled according to BI standards ([6](#)).

During the study conduct, protocol deviation should be monitored and guidance for improving / teaching the respective sites should be discussed during the study Medical Quality Review Meetings (MQRMs).

Table 6.2:1 Important protocol violations

Category/ Code		Description	Requirements	Excluded from
A [1]		Entrance criteria not met		
	A1	Diagnosis of trial disease questionable	Inclusion criteria IN2-IN4 not met. or Indicated by medical review of oncological history and baseline tumour assessment details from investigator.	None

Proprietary confidential information © 2017 Boehringer Ingelheim International GmbH or one or more of its affiliated companies

Table 6.2:1 Important protocol violations (cont.)

Category/ Code	Description	Requirements	Excluded from	
	A2	
Prohibited baseline condition, diagnosis or treatment
 
At least one of inclusion criteria IN6-IN9 or IN13 is not met
 
or
 
At least one of exclusion criteria EX3, EX7-EX8, EX10-EX12, EX14-EX16, or EX18-EX20 is met.
 
or
 
Indicated by medical review of baseline conditions.
 
or
 
Prohibited medication use (or surgery) before the treatment period of the trial, that is,
 
At least one of exclusion criteria EX1, EX2, EX4-EX6, EX9, EX22, or EX24 is met
 
or
 
Indicated by medical review of concomitant therapy use before start of study treatment.
	None	
	A3	
Laboratory result indicating inadequate organ function at screening
 
Inclusion criteria IN11 or IN12 not met
 
or
 
Both screening and baseline (defined in Section 6.7 of this document) laboratory results are missing.
	None	
	A4	Adequate archival tumour tissue not available	IN5 not met.	
B [1]		Legal Criteria		
	B1	Informed consent not available / not done	
Inclusion criterion IN14 is not met.
 
or
 
Date of informed consent is missing.
	All

Proprietary confidential information © 2017 Boehringer Ingelheim International GmbH or one or more of its affiliated companies

Table 6.2:1 Important protocol violations (cont.)

Category/ Code	Description	Requirements	Excluded from	
	B2	Informed consent too late	Informed consent date was after Screening Visit date	None
	B3	Age limit for patient inclusion not adhered to	Patient's age < 18 as in IN1	All
C [2]		Trial medication and randomisation		
	C1	Time window violation for procedures performed at screening	Baseline disease assessment not within 30 days prior to first treatment. Create listing, decision at MQRM / RPM.	None
	C2	Trial medication not given according to protocol	Dose reduction scheme not followed (see CTP section 4.1.4.3); Administration of trial medication(s) not compliant. Indicated by medical review (i.e. where Administration of xentuzumab according to the protocol = 'No' and associated comments, or compliance data from afatinib with associated comments) Please note: This excludes the investigational treatment given outside the boundaries specified in the CTP (covered in Category C3).	None
	C3	Infusion time for the investigational treatment outside of CTP specific boundaries	Infusion duration of xentuzumab given < 50 minutes or > 200 minutes (Infusion time should be from 60 to 180 minutes, but the thresholds above are accepted). The exact duration of the infusion should be calculated taking interruptions into account. In case of missing administration times, the violation will not be considered important if administration according to protocol = 'Yes'.	None

Proprietary confidential information © 2017 Boehringer Ingelheim International GmbH or one or more of its affiliated companies

Table 6.2:1 Important protocol violations (cont.)

Category/ Code	Description	Requirements	Excluded from	
	C4	Patient assignment not followed	Patients do not receive the initial treatment they were allocated to.	None
D [2]		Concomitant medication		
	D1	Prohibited treatment during trial conduct phase	Exclusion criterion EX17 met or Indicated by medical review of concomitant therapy use during study treatment.	None
E [2]		Missing Data		
	E1	Imaging assessments not done according to CTP instructions	Imaging assessment should be performed at screening and several time points thereafter (see TSAP Section 6.7.2).	None
	E2	Pregnancy test not done according to CTP instructions	Only for studies where pregnancy tests are required.	None
F [2]		Trial Specific protocol violations		
	F1	Other protocol violations affecting patient rights or safety	Manual PVs will be collectively captured.	None

[1] IPV will be derived automatically .

[2] IPV will be identified via individual review at MQRM/RPM/DBL.

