  - Absolute neutrophil count (ANC)  $\geq 1,500/\text{mm}^3$
  - Platelet count  $\geq 100,000/\text{mm}^3$
  - Estimated creatinine clearance  $> 45\text{ml/ min}$  [Appendix 10.2](#).
  - Total bilirubin  $\leq 1.5$  times upper limit of institutional normal.
  - Aspartate amino transferase (AST) and alanine amino transferase (ALT)  $\leq 3 \times$  upper limit of institutional normal (ULN) (if related to liver metastases  $\leq 5\times$ ULN)
13. Recovered from any previous therapy related toxicity to  $\leq$  Grade 1 at study entry (except for stable sensory neuropathy  $\leq$  Grade 2 and alopecia)
14. Written informed consent that is consistent with ICH-GCP guidelines and local regulation.

Proprietary confidential information.

© 2016 Boehringer Ingelheim International GmbH or one or more of its affiliated companies. All rights reserved.  
This document may not - in full or in part - be passed on, reproduced, published or otherwise used without prior written permission.

15. No known potentially targetable mutation other than IGF signalling pathway or EGFR or no available treatment for potentially targetable mutation

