(c) are not using an acceptable method of birth control (see [Section 4.2.2.3](#)) or do not plan to continue using this method throughout the study and/or do not agree to submit to pregnancy testing required by this protocol.

14. Any history of or concomitant condition that, in the opinion of the investigator, would compromise the patient's ability to comply with the study or interfere with the evaluation of the efficacy and safety of the test drug.
15. Previous or concomitant malignancies at other sites, except effectively treated non-melanoma skin cancers, carcinoma in situ of the cervix, ductal carcinoma in situ or effectively treated malignancy that has been in remission for more than 3 years and is considered to be cured.
16. Disease that is considered by the investigator to be rapidly progressing or life threatening such as extensive symptomatic visceral disease including hepatic involvement and pulmonary lymphangitic spread of tumour (subjects who are intended for urgent chemotherapy)
17. Requiring treatment with any of the prohibited concomitant medications listed in [Section 4.2.2](#) that cannot be stopped for the duration of trial participation.
18. Known pre-existing interstitial lung disease (ILD).
19. Any history or presence of poorly controlled gastrointestinal disorders that could affect the absorption of the study drug (e.g. Crohn's disease, ulcerative colitis, chronic diarrhoea, malabsorption).
20. Active hepatitis B infection active hepatitis C infection and/or known HIV carrier.
21. Use of alcohol or drugs incompatible with patient participation in the study in the investigator's opinion.
22. Previous treatment with agents targeting the IGF signalling pathway.
23. Patients unwilling or unable to comply with protocol in the opinion of the investigator
24. Previous treatment with EGFR TKI which can't be documented as either reversible or irreversible (Part B only)
25. Part B only: Prior treatment with third generation irreversible EGFR TKI (e.g. AZD9291 or CO-1686)

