### 7.3 PLANNED ANALYSES

All patients who are treated with at least one single dose of Xentuzumab (BI 836845) or afatinib will be included in all efficacy and safety analyses.

During Part A, cohorts of patients treated with Xentuzumab (BI 836845) in combination with afatinib will be evaluated continuously based on the totality of the safety data in order to determine the MTD and the RP2D.

Summary outputs of efficacy analyses will include all patients entered in Part B of the trial and patients entered in RP2D level in Part A. All endpoints defined in [Section 5.1.1](#) will be summarized descriptively.

Safety analysis will be summarized separately for patients treated in Part A and Part B.

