6.3 PATIENTS SETS ANALYSED

The following analysis sets will be defined for this trial:

- Enrolled set (ENR)

This patient set includes all patients with informed consent given. The enrolled set will be used for patient disposition tables.

- Treated set (TS)

This patient set includes all patients who are documented to have received and taken at least one dose of any study medication during the treatment cycles (from day 1).

Proprietary confidential information © 2017 Boehringer Ingelheim International GmbH or one or more of its affiliated companies

The TS will be used for all planned safety and efficacy analyses.

- **MTD Set (MS)**

The MTD set defines the set of patients in the first part of the trial that are fully evaluable for determination of the MTD in the first treatment course. The MTD set will be used for some safety analyses in the first part, this is specified in the technical TSAP.

Patients in the TS who were replaced within the MTD evaluation period in the first part of the trial will be excluded from the determination of the MTD. Replacement of patients in the first part of the study is defined in Section 3.3.4.3 of the CTP. The final list of replaced patients is supplied by the Trial Clinical Monitor (TCM) no later than the last report planning meeting before the database lock for the safety analysis.

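### SAP 6.2 drops treated patients with a missing consent date or age under 18 from every analysis, against protocol 7.3 and SAP 6.3, and its automatic eligibility codes omit EX25 and IN15

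*SAP*

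**What the plan says.** **Who is analysed.** Protocol 7.3 says that every patient given at least one dose of either drug "will be included in all efficacy and safety analyses". It states no exception. SAP 6.3 defines the treated set (TS) in the same way, also without exception, and adds: "The TS will be used for all planned safety and efficacy analyses".

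**Who is removed.** SAP 6.2 plans no per-protocol analysis and says that "no patient will be excluded from the analyses (except those with missing informed consent or not adhering to age limit"). In Table 6.2:1 two codes have All in the exclusion column:
- B1, consent not available or not done. It is triggered if IN14 is not met or, as an alternative, if "Date of informed consent is missing".
- B3, age below 18 (IN1).

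The footnote for categories A and B reads "IPV will be derived automatically".

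**Which eligibility breaches are named.** Code A2 covers prior treatment with "At least one of exclusion criteria EX1, EX2, EX4-EX6, EX9, EX22, or EX24 is met", plus a second list of exclusion criteria and inclusion criteria IN6 to IN9 and IN13. Two protocol criteria appear under no code:
- EX25: "Part B only: Prior treatment with third generation irreversible EGFR TKI (e.g. AZD9291 or CO-1686".
- IN15: "No known potentially targetable mutation other than IGF signalling pathway or EGFR or no available treatment for potentially targetable mutation".

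The amendment log in protocol section 11 shows that amendment 1 (15 Jul 2015) added both. The SAP is dated 27 Sep 2017.

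**The concern.** There are two separate points.

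The first is a contradiction about the analysis population. A programmer who builds the tables from SAP 6.3 keeps a dosed patient whose consent date is blank; one who builds them from Table 6.2:1 deletes that patient. What is at stake is an exposed patient's adverse events and tumour response leaving every table. The cause could be a blank field although consent was given, or an age error at entry. An eligibility error is not normally a reason to drop safety data from someone who received the drug, and the SAP does not do so for its other eligibility breaches.

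The second is completeness. With no per-protocol analysis, the violation table and listing in SAP 7.1.2 are the planned record of who was treated outside the criteria. If EX25 and IN15 are not in the automatic derivation, that record depends on someone noticing the breach by another route. EX25 is the more material of the two because it is a Part B criterion, and Part B carries the response endpoint.

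**Working it through.** **1. Set the population rules side by side.**

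| Place | Dosed patient, IN14 met, consent date blank | Dosed patient, age under 18 |
|---|---|---|
| Protocol 7.3 | Kept in all efficacy and safety analyses | Kept |
| SAP 6.3, treated set | Kept | Kept |
| SAP 6.2, sentence | Unclear: refers to missing consent, not a missing date | Removed |
| SAP Table 6.2:1 | Removed (B1) | Removed (B3) |

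The table contradicts the first two rows in both columns. In the first column it also goes further than the sentence it implements.

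**2. Compare with neighbouring rows of Table 6.2:1.** Consent dated after the screening visit (B2) removes nobody. Eligibility codes A1 to A3 have None. Code C3 does not treat missing infusion times as important when the administration is recorded as given per protocol. B1 has no matching safeguard for a missing date when IN14 is recorded as met.

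**3. Check the criteria against the codes.** The protocol has IN1 to IN15 and EX1 to EX25. Table 6.2:1 names IN1 to IN9, IN11 to IN14, EX1 to EX12, EX14 to EX20, EX22 and EX24. The difference is IN10, IN15, EX13, EX21, EX23 and EX25. The point is confined to IN15 and EX25. IN10, EX21 and EX23 rest on the investigator's opinion, and EX13 is partly covered by code E2 on pregnancy tests. By contrast EX3 and EX24, the other Part B-only exclusions, are both named in A2, and no reason is given for leaving EX25 out.

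**4. Reproduce the plan's own figure.** Protocol 7.6 gives 73% for at least 3 responses in 18 patients at a true rate of 20%.

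P(X ≥ 3) = 1 − Σ(k = 0 to 2) C(18,k) × 0.2^k × 0.8^(18−k) = 1 − (0.01801 + 0.08106 + 0.17226) = 0.7287 (protocol table: 0.72866).

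**5. Illustrate a removal.** The documents give no count of B1 or B3 cases, so one or two Part B removals is an assumption made only to show scale.

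| Part B patients analysed | P(X ≥ 3) at 20% |
|---|---|
| 18 | 0.729 |
| 17 | 0.690 |
| 16 | 0.648 |

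For the observed rate, start from 3/18 = 16.7%:
- remove one non-responder: 3/17 = 17.6%, about +1.0 point;
- remove one responder: 2/17 = 11.8%, about −4.9 points.

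**6. Effect of naming EX25 and IN15.** Codes A1 to A3 carry None, so a flagged patient stays in the analysis. The change in N is 0 and the change in response rate is 0 points.

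**The case against.** **On consent and age.** B1 sits under legal criteria, and excluding a patient who never gave valid consent may have a legal basis. Protocol 8.1 requires each signature on the consent form to be personally dated, so a missing date can be a real consent defect and not only a data-entry gap. Automatic derivation describes how a flag is raised; the handling follows company standards that are not available here, and a blank date may well be queried first. SAP 6.2 states its exception openly. Imputation will not trigger B3 wrongly, because a birth date known only by year becomes 1 January, which makes the patient older. Expedited reporting of serious events is separate from these tables. All of this stands. It supports keeping an exclusion for documented absence of consent. It does not reconcile the table with protocol 7.3 or SAP 6.3, and it does not justify removal on a blank date alone when IN14 is met.

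**On EX25 and IN15.** A reader might infer that such breaches can never be listed. The documents do not support that. A1 and A2 have medical-review triggers covering oncological history, baseline conditions and earlier therapy. Protocol 5.3.4 collects prior TKI treatment with dates. F1 takes manual violations, although its title limits it to those affecting patient rights or safety. SAP 6.2 calls the list a working list, open until the last planning or lock meeting. A list of important violations is also partly a matter of judgement. What stands of the point is that the automatic route is incomplete.

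**Other inferences that go too far.**
- That EX25 and IN15 define the Part B population. IN15 applies to both parts, and Part B is defined mainly by IN4 and IN6, both of which are named.
- That an unflagged patient shifts the response rate by 1/18. That patient remains in the analysis, so the shift is zero.
- That the departure from the protocol is undeclared. Only subsection 4.3 of SAP section 4 is visible, so this cannot be said.

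**Conclusion.** The contradiction is real. Table 6.2:1 removes B1 and B3 patients from all analyses, while protocol 7.3 and SAP 6.3 keep every dosed patient. B1 is also broader than the SAP 6.2 sentence. The possible loss is one exposed patient's safety and response data per case. In Part B, one removal from 3/18 would move the observed rate to 17.6% or 11.8%, depending on whether the patient removed had responded. These figures assume 3 responders and one removal; the true number of cases is unknown and may be zero.

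The omission of EX25 and IN15 from the automatic codes is also real, but it is a reporting gap only, with other routes by which a breach could still be recorded. It does not affect N or the response rate.

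Both points are worth correcting before database lock because the edits are small. Neither shows that any result is wrong.

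**What to change.** 1. **B1.** Limit the exclusion to documented absence of valid consent. Where only the date is missing, query it and list the patient, who stays in the treated set.
2. **B3.** Set the exclusion column to None, or otherwise reconcile the code with protocol 7.3 and SAP 6.3 so that treated patients stay in the safety analyses.
3. **SAP 6.2 and 6.3.** Align the 6.2 sentence with the revised table. If any exclusion for absent consent is kept, state it in the treated-set definition and as a departure from protocol 7.3.
4. **A2.** Add EX25 and IN15, with None in the exclusion column.

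The cost is edits to one SAP table, the sentences that refer to it and its derivation program. SAP 6.2 leaves the list open until before database lock, so the edits fit the existing process. No new data are needed beyond resolving any queries on missing consent dates.
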